2.1 Objectives & Hypotheses

Objective:

To compare rates of etonogestrel implant discontinuation in implant initiators who are given advance provision of combined oral contraceptive pills (COCs) and a bleeding rescue regimen (COCR intervention) to participants given standard counseling (comparator).

Secondary Objectives:

1. To determine if participants initiating the contraceptive implant who are also provided COCR are more likely than participants receiving standard counseling to:
 - a. report higher levels of satisfaction with their contraceptive implant at one year following initiation
 - b. require less clinical follow-up and clinical resources in the year following initiation.
2. To determine if people who did not enroll in this randomized controlled trial are similar in characteristics and outcomes to the enrolled group and specifically compared to the “usual care” arm.

Primary Hypothesis: We hypothesize that participants who initiate the contraceptive implant and are given advance provision of COCR will be significantly less likely to discontinue their implant in the year following insertion than those given standard counseling

Secondary Hypothesis: We hypothesize that participants who initiate the contraceptive implant and receive the COCR intervention will:

- a. be more satisfied with their contraceptive implant
- b. make and attend fewer follow-up visits in the year after initiation.

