2.7 Statistical Analysis and Sample Size Justification

[name] (Co-Investigator) will be responsible for analyzing the study data. This study is a non-blinded randomized controlled trial. Because this study involves standard clinical care, study arm will be identified in the electronic medical record and will be known to investigators and providers. However, no data will be aggregated or analyzed until study completion.

Variables:

The primary outcome variable will be retention of the contraceptive implant at 12 months post-insertion. Discontinuation will be determined through participant report at the 3, 6, and 12 month follow-up and by review of medical records.

Secondary outcome variables include:

Variable	Assessed by:
Satisfaction with bleeding profile	Likert scale ("very satisfied", "somewhat satisfied" and "not satisfied")
Satisfaction with method overall	Likert scale ("very satisfied", "somewhat satisfied" and "not satisfied")
Likelihood of recommending implant to a friend	Likert scale ("very likely," "somewhat likely" "not at all likely")
Follow up related to implant (visits or phone calls)	EMR review
Side effects attributed to implant	Phone/online survey

Additional variables include:

Variable	Assessed by:
Age	EMR
Race/Ethnicity	EMR
BMI	EMR

Statistical Methods

We will use standard bivariate statistics including Student's t-tests and non-parametric medians tests to compare continuous variables. We will use Chi-squared and Fisher's exact tests to compare dichotomous and categorical variables. The primary outcome will be analyzed using the Chi-squared test to generate an odds ratio and confidence intervals for continuation by study arm. Backwards stepwise logistic regression will be performed to identify independent predictors of implant discontinuation. In the first step, demographic variables will be included if they have a significant bivariate relationship to the outcome ($p < 0.1$). In the second step, each reproductive characteristic will be considered as a candidate predictor and included if it significantly ($p < 0.1$) improves upon the fit of the model from the first step. Study arm will be included in the third, final step. We will also compute estimates of time to discontinuation using Cox regression models.

Multiplicity

If necessary, we will use the Bonferroni method to correct for multiple comparisons.

Power/Sample Size:

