Over the last 10 years BC4U clinic has placed approximately 1,200 implants per year. We anticipate that we will be able to enroll a total of 600 of the 1200 implant initiators (50%). Participants will be randomized in a 1:1 ratio. Thus, we will

	randomize 300 participants to each arm. Based on prior studies in this clinic (Richards 2017, Cohen 2017, Cohen 2019, Green 2019) , we hypothesize that 25% of participants in the SC arm will discontinue the implant within 12 months and 15% of participants in the COCR group will. With a loss-to-follow-up rate of 17% (from prior studies), we will have 80% power to detect this 10 percentage-point difference with a two-sided alpha of 0.05.
2.8 Specific Drug Supply Requirements	Nexplanons for this study will be purchased by BC4U clinic of Children's Hospital Colorado under the 340B program as per clinical standard of care. COCs for this study will be purchased by the BC4U clinic of Children's Hospital Colorado under the 340B program as per clinical standard of care. No drugs will be supplied by MSD.
2.9 Adverse Experience Reporting	We will use the Model Study Agreement reporting requirements for adverse events.
2.10 Itemized Study Budget	A preliminary study budget must be provided with the initial proposal submitted to give guidance to the MISP Review Committee as to the expected study costs. A refined itemized budget detailing the costs associated with the study should be provided with the final protocol or included in the study agreement as Exhibit B.

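### The three ordered satisfaction-type outcomes are covered only by an unordered chi-squared/Fisher test, which is valid but less powerful than an ordinal test for the stated directional hypothesis

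*Combined protocol and SAP*

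**What the plan says.** The outcome table in section 2.7 of the combined protocol and SAP includes three items with three ordered answers. Satisfaction with bleeding profile and "Satisfaction with method overall" run from very, through somewhat, to not satisfied. Likelihood of recommending the implant to a friend runs from very, through somewhat, to not at all likely.

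Under Statistical Methods, t-tests and medians tests are assigned to continuous variables, and Chi-squared and Fisher's "exact tests to compare dichotomous and categorical variables". The logistic and Cox models are described for discontinuation only. No rank, trend or ordinal method is named, and tests are not assigned outcome by outcome, so the three items fall under the categorical sentence by default.

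Secondary objective 1a in section 2.1 asks whether COCR participants are more likely to "report higher levels of satisfaction with their contraceptive implant at one year following initiation". The matching secondary hypothesis also points one way: greater satisfaction with COCR.

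Section 2.3 surveys all participants at 3 months, 6 months and one year. It covers satisfaction with the implant and with bleeding, and it also records the contraceptive method used after the implant.

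**The concern.** A chi-squared or Fisher test on a two-by-three table gives the same result however the columns are ordered. It looks for any difference between the arms, while the hypothesis is about movement along the scale. If the true effect is such a movement, the second degree of freedom adds noise and no signal.

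The plan also provides no single effect estimate for these items. A significant 2-df test says that the distributions differ, but not by how much or in which direction.

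At stake are the chance of detecting a real improvement in satisfaction, and whether the result can be reported as one interpretable number with an interval.

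**Working it through.** **1. The plan's own figure.** The inputs are in section 2.7: "25% of participants in the SC arm will discontinue the implant within 12 months", "15% of participants in the COCR group will", "Participants will be randomized in a 1:1 ratio" with 300 per arm, 17% loss to follow-up, and a "two-sided alpha of 0.05". The stated result is "we will have 80% power to detect this 10 percentage-point difference".

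- Evaluable per arm: 300 × 0.83 = 249.
- Standard error under no difference: √(2 × 0.20 × 0.80 / 249) = 0.03585.
- Standard error under the alternative: √((0.25 × 0.75 + 0.15 × 0.85) / 249) = 0.03557.
- z = (0.10 − 1.96 × 0.03585) / 0.03557 = 0.836, so power is 79.8%.

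The stated 80% reproduces. It concerns discontinuation only; no power is stated for any satisfaction outcome.

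**2. Cost of the second degree of freedom, with no response distribution assumed.**

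- A 1-df test at two-sided 0.05 has 80% power when its non-centrality is (1.960 + 0.842)² = 7.85.
- If the whole effect lies in the ordered direction, the 2-df chi-squared test has the same non-centrality but a critical value of 5.99. Its power is 70.9%.
- Restoring 80% on 2 df needs 1.23 times that non-centrality, which means about 23% more participants.

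**3. Power for three-level items.** The documents give no satisfaction distribution or effect size, so both are assumed here and varied. The SC split (very/somewhat/not) is shifted by multiplying each cumulative odds by a common odds ratio. For example, with 40/35/25 and an odds ratio of 1.5:

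- 0.40 has odds 0.667, which become 1.00, giving 0.50.
- 0.75 has odds 3.00, which become 4.50, giving 0.818.
- The COCR split is therefore 50.0/31.8/18.2.

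The table gives power (%) from 40,000 simulated trials per cell, 249 per arm, two-sided 0.05. Each cell shows the Pearson 2-df test first, then the tie-corrected Wilcoxon rank-sum test.

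| SC split | OR 1.4 | OR 1.5 | OR 1.6 | OR 1.8 |
|---|---|---|---|---|
| 40/35/25 | 41.7 / 51.9 | 56.9 / 67.3 | 69.9 / 79.2 | 88.6 / 93.5 |
| 50/30/20 | 39.6 / 49.6 | 54.5 / 65.0 | 67.2 / 77.4 | 86.2 / 91.7 |
| 60/25/15 | 35.4 / 44.8 | 49.1 / 59.8 | 61.7 / 71.9 | 80.8 / 88.0 |
| 34/33/33 | 42.3 / 52.7 | 58.5 / 68.9 | 72.0 / 80.9 | 89.6 / 94.3 |
| 25/50/25 | 41.2 / 51.6 | 56.5 / 66.9 | 70.2 / 79.3 | 88.1 / 93.1 |

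The loss is 8.9 to 10.7 points at odds ratios 1.4 to 1.6, and 4.7 to 7.2 points at 1.8. With no effect, both tests reject in about 5% of trials.

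**4. Dichotomising.** With 40/35/25 and an odds ratio of 1.5, comparing very satisfied with the rest has 61.9% power, and comparing not satisfied with the rest has 45.3%. The rank test has 67.3%. The rank test was ahead of both cuts in every shifted scenario in the table.

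**5. A change that is not a shift.** With SC 40/30/30 against COCR 30/45/25, the unordered test has 89% power and the rank test 13%.

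**The case against.** The planned test is not an error. It holds its 5% level, and the plan claims no power for satisfaction. The 2 df is inferred: section 2.7 assigns no test item by item, and an item collapsed to two levels would have 1 df. However, no collapsing rule is given, and in the shifted scenarios collapsing also loses power. For a non-monotone change the unordered test is far better, as step 5 shows, but section 2.1 does not hypothesise that. The 249 per arm is borrowed from discontinuation, which medical records also inform. Satisfaction comes from surveys alone, so the evaluable number could be smaller. All of this stands, and it makes the point one of efficiency.

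A reader might go further and infer that satisfaction will be compared only among women who still have the implant. With 25% against 15% expected to discontinue, that would select on the primary outcome and could even reverse the comparison. The documents do not support this inference. Section 2.3 surveys everyone, and recording the post-implant method implies contact after removal. No section proposes a current-user analysis. A reversal can be constructed only by assuming satisfaction levels that the documents do not give. What is true is narrower: the plan does not state the analysis set for these items, and one sentence would settle it.

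Nor does section 2.1 rank satisfaction above follow-up visits, so it should not be read as the leading secondary hypothesis.

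**Conclusion.** The point holds as a question of efficiency in the secondary analyses. Ordered outcomes and a directional hypothesis are matched only with an unordered test. For an effect wholly in the ordered direction, 80% power falls to about 71%. With 249 per arm, the loss is about 9 to 11 points at odds ratios of 1.4 to 1.6 and 5 to 7 at 1.8.

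These sizes rest on assumed response distributions, a proportional-odds shift, an uncorrected two-sided 0.05 for each item, and survey response as good as the follow-up assumed for the primary outcome. Lower response, or the Bonferroni correction that section 2.7 allows for, would reduce power for both tests. The primary analysis and the sample size are not affected.

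**What to change.** In section 2.7, state that the three Likert items at 12 months are compared with a proportional-odds model, reporting a common odds ratio with its confidence interval, or with a Wilcoxon rank-sum test. Keep the test two-sided. State that the comparison is by assigned arm and includes every randomised participant who answers the survey already planned for all, whether or not the implant is still in. Use the answers given. Scoring every removal as not satisfied would build the expected 25% against 15% difference in the primary outcome into the secondary one.

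Report the three-level distribution by arm beside the model and check the proportional-odds assumption. That also covers the small downside, which is lower power for a non-monotone change.

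The cost is a few sentences of SAP text, with no extra visits, participants or data items.

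### The predictor model in section 2.7 selects on p<0.1 and makes no allowance for that selection, so its intervals for null or weak predictors are not valid

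*Combined protocol and SAP*

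**What the plan says.** All of this is in section 2.7 of the combined protocol and SAP.

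- **Primary analysis.** It is unadjusted: "The primary outcome will be analyzed using the Chi-squared test to generate an odds ratio and confidence intervals for continuation by study arm".
- **Purpose of the regression.** "Backwards stepwise logistic regression will be performed to identify independent predictors of implant discontinuation".
- **Step 1.** "In the first step, demographic variables will be included if they have a significant bivariate relationship to the outcome", with p<0.1 as the threshold.
- **Step 2.** Each reproductive characteristic is a candidate, "included if it significantly ($p < 0.1$) improves upon the fit of the model from the first step".
- **Step 3.** "Study arm will be included in the third, final step". No significance condition is attached to arm.
- **Time to event.** "We will also compute estimates of time to discontinuation using Cox regression models". No covariates are named.

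The table of additional variables lists age, race/ethnicity and BMI. It lists no reproductive characteristic. The multiplicity paragraph offers a Bonferroni correction only if it proves necessary.

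**The concern.** The stated product of this model is a list of independent predictors of discontinuation. Each predictor is on the list because its association looked strong enough in these same data. A standard confidence interval assumes that the variable would have been reported whatever the data showed. Once that fails, the interval is too optimistic and the estimate is pushed away from zero, most of all for variables with little or no effect. A clinic could then counsel, or plan further work, on predictors that are noise or are overstated.

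Two gaps in the text add to this:

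- **Algorithm.** Backward elimination starts from a full model and removes terms. The steps described screen variables and then add them. Two analysts could fit different models from the same paragraph.
- **Candidates.** Because the reproductive characteristics are not named, the pool could be settled after outcomes are known.

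**Working it through.** **Inputs from section 2.7.** 300 randomised per arm; 17% loss to follow-up; two-sided alpha 0.05; "25% of participants in the SC arm will discontinue the implant within 12 months" and 15% in the COCR arm; entry threshold p<0.1.

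**Assumptions not in the documents.** Eight candidates (three demographic, five reproductive), independent and standard normal, with log odds ratios from 0 to 0.4 per SD.

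**1. The plan's own figure.** Evaluable per arm: 300 × (1 − 0.17) = 249, so 498 in total.

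Power = Φ{[0.10 − 1.96 × √(2 × 0.20 × 0.80 / 249)] / √[(0.25 × 0.75 + 0.15 × 0.85) / 249]} = Φ{(0.10 − 0.0703) / 0.0356} = Φ(0.836) = 79.8%.

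The stated 80% reproduces. It rests on the unadjusted comparison, so nothing below changes it.

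**2. Null predictors, by formula.** A null variable is selected when |z| > 1.645 (probability 0.10). Its 95% interval misses zero when |z| > 1.96 (probability 0.05). Coverage given selection is therefore 1 − 0.05/0.10 = 50%.

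**3. Weak predictors, by formula.** With 20% of participants discontinuing overall, the SE of a log odds ratio per SD is about 1/√(498 × 0.2 × 0.8) = 0.112. A true value of 0.1 has expected z = 0.1/0.112 = 0.893.

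- P(selected) = P(Z > 1.645 − 0.893) + P(Z < −1.645 − 0.893) = 0.226 + 0.006 = 0.232.
- P(selected and covered) = P(0.752 < Z < 1.96) = 0.226 − 0.025 = 0.201.
- Coverage given selection = 0.201/0.232 = 87%.
- Mean selected estimate = 0.1 + 0.112 × (0.301 − 0.016)/0.232 = 0.24, where 0.301 and 0.016 are normal densities at 0.752 and 2.538.

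**4. Simulation of the three steps** (1,500 runs per scenario, assumptions as above):

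| True log odds ratio per SD | Coverage, selected predictors | Mean selected estimate |
|---|---|---|
| 0 | 52% (fixed model 94%) | – |
| 0.1 | 85% (fixed model 95%) | 0.24 |
| 0.2 | 95% | 0.29 |
| 0.3 to 0.4 | about 97% | 0.34 and 0.43 |

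Steps 2 and 3 agree with the simulation to within two percentage points.

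**5. False entries when all eight are null.** By formula, at least one enters with probability 1 − 0.9^8 = 57% (simulated 61%). At least one is significant at 0.05 with probability 1 − 0.95^8 = 34% (simulated 36%). The second figure is mainly multiplicity: a fixed model with eight null terms would carry about the same risk, but would show all eight.

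**6. Effect on the arm estimate.** The planned odds ratio is (0.15/0.85)/(0.25/0.75) = 0.53. Over 3,000 runs per scenario at that effect:

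- The selection rule produced 102 to 256 different covariate sets.
- The arm log odds ratio differed from the fixed-covariate model by 0.019 to 0.023 on average, against an SE of about 0.24.
- Coverage for arm was 94.7% to 95.2% with selection and 94.4% to 95.1% with fixed covariates.
- With no arm effect, type I error was 4.7% to 5.4% with selection and 4.8% to 5.3% with fixed covariates.

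**7. Room for a fixed model.** Expected discontinuations: 249 × 0.25 + 249 × 0.15 = 99.6. Arm plus eight single-parameter covariates gives 99.6/9, or about 11 events per parameter. Race/ethnicity may need more than one parameter.

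**The case against.** The strongest reply is that this is a secondary model with a descriptive aim. The trial's conclusion rests on the chi-squared test, the p<0.1 rule is itself written down in advance, and analysis waits until study completion. All of that stands, and it keeps the severity low.

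A reader might go further and infer that the treatment effect depends on stepwise selection, or that entering arm last is a fault. The documents support neither. Arm enters unconditionally, and its coefficient in the final model does not depend on the order of entry. Because selection runs without arm in the model, covariates are not chosen for what they do to the arm estimate. The measured shift is under a tenth of a standard error, with coverage and type I error essentially unchanged.

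The reply does not rescue the predictor results. Writing the selection rule down in advance does not make the intervals valid after it is applied. A conditional Bonferroni correction does not, as described, address the exaggerated estimates. Finding predictors is what this model is for, so calling it secondary does not answer a fault in that result. The candidate list also remains open.

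**Conclusion.** Wrong as written, for the error bars of the selected predictors; severity minor. Under the stated assumptions the failure is concentrated in null and weak predictors: coverage is about 52% and 85% against a nominal 95%, and estimates at 0.1 per SD are more than doubled. At 0.2 per SD coverage is nominal but the mean estimate is still high (0.29). At 0.3 to 0.4 there is little harm. The figures depend on the assumed number, strength and independence of the candidates. The 50% limit for a null variable does not: it follows from the 0.10 and 0.05 thresholds.

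The mislabelled algorithm and the unnamed reproductive characteristics can be seen from the text alone and must be resolved in any case. Nothing here supports a claim of a biased primary result, inflated type I error for arm, or insufficient power.

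**What to change.** 1. Replace the three-step selection with one prespecified logistic model containing study arm, age, BMI, race/ethnicity and any reproductive characteristics named in the SAP before analysis. Use the same covariates in the Cox model.
2. Report every predictor in that model, and the adjusted arm estimate, from that one fit.
3. Add the chosen reproductive characteristics to the variable table.
4. If a stepwise search is kept, describe the algorithm actually used, label it exploratory, and state that its p-values and intervals are not confirmatory.

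The cost is SAP wording and possibly a few fields from the chart; whether the chart holds them is an assumption. No extra participants or visits are needed, and the sample size does not change. One consequence should be stated in the SAP: the adjusted odds ratio is conditional on the covariates, so it is not the same quantity as the primary unadjusted odds ratio and the two need not agree exactly.

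### The multiplicity rule is optional and names no family of tests; stating that the primary is tested alone at 0.05 and using Holm for the secondary outcomes would settle it at almost no cost

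*Combined protocol and SAP*

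**What the plan says.** Section 2.7 of the combined protocol and SAP names one primary outcome, implant retention at 12 months, tested by chi-squared. It then tabulates five secondary outcomes: satisfaction with bleeding, satisfaction overall, likelihood of recommending the implant, implant-related follow-up, and side effects. The list is introduced in a way that leaves it open. Under Multiplicity there is a single sentence: "If necessary, we will use the Bonferroni method to correct for multiple comparisons".

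The Power/Sample Size text assumes that "25% of participants in the SC arm will discontinue the implant within 12 months" and "15% of participants in the COCR group will". It plans to "randomize 300 participants to each arm", allows 17% loss to follow-up, and states "80% power to detect this 10 percentage-point difference with a two-sided alpha of 0.05". No power, effect size or adjusted alpha is given for any secondary outcome.

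Section 2.1 attaches hypotheses to satisfaction and to follow-up visits. Sections 2.1 and 2.5 also set out a separate aim comparing enrolled with non-enrolled patients, which has its own primary outcome.

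**The concern.** The multiplicity sentence fixes nothing. Correcting every test, some of them or none would all comply with it. Section 2.7 says that no data are aggregated or analyzed before study completion, which rules out interim looks. It does not settle the correction rule before the final p-values are visible.

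The number of comparisons is also unclear. Section 2.3 collects satisfaction and side effects at 3, 6 and 12 months. The follow-up row covers visits or phone calls. Discontinuation by arm is examined by chi-squared, stepwise logistic regression and Cox models.

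Two things are at stake. If the primary test were drawn into a correction, the trial would no longer have the power it was sized for. If no correction were made, claims on the secondary outcomes would carry no control of the family-wise error. Where correction is used, a procedure that is at least as powerful under the same assumptions is available.

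**Working it through.** **Inputs (section 2.7, Power/Sample Size).** Discontinuation 25% (standard care) and 15% (COCR); 1:1 allocation; 300 randomized per arm; 17% lost; two-sided alpha 0.05. Evaluable per arm: 300 × 0.83 = 249.

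**Step 1. Reproduce the stated power.** Normal approximation with pooled variance under the null and no continuity correction:

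power = Φ[(|p1 − p2| − z × SE0) / SE1], where z is the two-sided critical value at the alpha in use

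- SE0 = √(2 × 0.20 × 0.80 / 249) = 0.03585
- SE1 = √((0.25 × 0.75 + 0.15 × 0.85) / 249) = 0.03557
- At alpha 0.05, z = 1.960: (0.10 − 1.960 × 0.03585) / 0.03557 = 0.836, and Φ(0.836) = 79.8%

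The exact binomial power of the uncorrected chi-squared test is 80.1%. The stated 80% is reproduced, with nothing to spare.

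**Step 2. Power of the primary test if it were inside a Bonferroni family.** Same formula, alpha = 0.05/k:

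| Tests in family (k) | Alpha | z | Power at 249 per arm |
|---|---|---|---|
| 1 | 0.05 | 1.960 | 79.8% |
| 2 | 0.025 | 2.241 | 71.0% |
| 3 | 0.0167 | 2.394 | 65.5% |
| 6 (primary plus five secondary) | 0.0083 | 2.638 | 56.1% |

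Restoring 80% would need 303 evaluable per arm at k = 2 (366 randomized) and 387 at k = 6 (467 randomized, 934 in total against 600 planned).

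**Step 3. Secondary outcomes with no correction.** For five independent tests at 0.05 with no real effects, the family-wise error is 1 − 0.95^5 = 22.6%. By simulation with equal correlation between the five, it is about 21% at 0.3 and 18% at 0.5. Three of the five rows are related ratings of the same implant, so the independence figure is an upper value here.

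**Step 4. Bonferroni against Holm for five secondary outcomes.** The documents give no secondary power, so assume that each real effect has 80% power at 0.05, a mean z of 1.960 + 0.842 = 2.802. Bonferroni over five uses alpha 0.01, z = 2.576: Φ(2.802 − 2.576) = 58.9% per outcome. Holm was simulated with 400,000 sets of five z-statistics at correlations 0 to 0.5:

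| Real effects among the five | Bonferroni | Holm | Gain (points) |
|---|---|---|---|
| One | 59% | 59% | about 0 |
| Two | 59% | 61% | about 2 |
| Five | 59% | 69-70% | about 10-11 |

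That Holm never rejects less than Bonferroni follows from its construction: its smallest threshold equals Bonferroni's, and the later ones are larger. Only the size of the gain depends on the assumed effects.

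**The case against.** A reader might infer that the multiplicity sentence contradicts the 80% power claim. The documents do not support that. There is one primary outcome with one main test, powered at the full two-sided 0.05, and nothing says that Bonferroni covers it. The natural reading leaves it uncorrected, so the 71% and 56% figures describe a reading that the plan's own alpha argues against. What remains is that the plan never says so.

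A reader might also infer that the decision to correct will be taken after the data are seen. No passage says this. The plan leaves that route open, so it could happen.

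A third tempting reading is that Bonferroni wastes power on the secondary outcomes. Bonferroni is a valid method, it may never be applied, and the plan claims no secondary power that could be lost. The 10-11 point gain is the case most favourable to Holm; with one real effect the gain is nil. Bonferroni also gives simple simultaneous confidence intervals, which Holm does not readily give. These points limit the size of the concern. They do not remove the reason to prefer Holm for testing, since it costs nothing in assumptions or error control.

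Finally, a rule that names five outcomes without fixing a time point would leave the family undefined, and one that calls everything else exploratory would demote the enrolled versus non-enrolled aim. Both objections stand, and the replacement text has to meet them.

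**Conclusion.** The point holds as a gap in pre-specification together with a cheap improvement in method. The text contains no internal contradiction, and the sample size does not need to change.

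The primary power claim is correct on its natural reading and should be protected by saying that the primary test stands outside any correction. The loss would be about 9 points in a family of two (79.8 − 71.0) and about 24 in a family of six (79.8 − 56.1). Those figures rest only on the plan's own rates, loss to follow-up and alpha.

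For the secondary outcomes, leaving five tests uncorrected implies a family-wise error of about 18-23% at correlations from 0.5 down to 0. Holm's gain over Bonferroni is about 0 to 11 points per real effect. The gain rests on the assumed 80% unadjusted power and the number of real effects, neither of which the documents give, so it is illustrative.

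**What to change.** Replace the Multiplicity sentence in section 2.7 with:

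> The primary outcome is tested alone at two-sided 0.05 without correction. The five secondary outcomes listed in 2.7, each tested once at 12 months, form one family tested by the Holm step-down procedure at family-wise 0.05. The comparison of enrolled with non-enrolled patients is a separate secondary aim with its own primary outcome and is reported separately. Other comparisons are exploratory, with 95% confidence intervals.

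For this to define five tests, each row needs one measure. In particular, the follow-up row should say how visits and phone calls over the 12 months are combined.

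The cost is a few lines of text, with no extra participants or data. There are two small downsides: some nominally significant secondary results will not be claimed, and Holm does not readily supply simultaneous confidence intervals.
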